2.6 Sample Size and Power

For primary analyses of outcomes there will be no direct statistical testing between study arms or between study arms and the data presented in MTN-042B. Instead, the frequency of primary and secondary outcomes from MTN-042 will be viewed in the context of local background pregnancy outcome data compiled in the MTN-042B study, a multi-site, cross-sectional chart review of pregnancy outcome data from the same four African sites. It is hypothesized that participants who use Truvada oral tablet daily and insert the DPV vaginal matrix ring (25 mg) once every 4 weeks will experience distributions of pregnancy outcomes that are qualitatively similar to the general population (i.e. the data compiled in MTN-042B). Comparisons to MTN-042B will not be included in the Clinical Study Report (CSR).

To characterize the statistical properties of this study, the below presents the probability of observing zero, at least one, ten or more, and fifty or more safety endpoints in each group by cohort size and among the total study population for various “true” event rates, ranging from low to high:

Table 1. Probability (%) of observing an event given different “true” event rates by cohort size

“True” event rate	P (0 events)		P ≥ 1 event		P (≥ 10 events)		P (≥ 50 events)	
Cohorts 1-2^a	n=100	n=50	n=100	n=50	n=100	n=50	n=100	n=50
1%	36.6	60.50	63.40	39.50	0.00	0.00	0.00	0.00
5%	0.59	7.69	99.41	92.31	1.15	0.00	0.00	0.00
10%	0.00	0.52	100.00	99.48	41.68	0.94	0.00	0.00
15%	0.00	0.03	100.00	99.97	90.06	11.99	0.00	0.00
25%	0.00	0.00	100.00	100.00	99.99	73.78	0.07	0.00
Cohort 3^a	n=200	n=50	n=200	n=50	n=200	n=50	n=200	n=50
1%	13.4	60.50	86.6	39.50	0.00	0.00	0.00	0.00
5%	0.00	7.69	100.00	92.31	41.69	0.00	0.00	0.00
10%	0.00	0.52	100.00	99.48	99.19	0.94	0.00	0.00
15%	0.00	0.03	100.00	99.97	100.00	11.99	0.01	0.00
25%	0.00	0.00	100.00	100.00	100.00	73.78	46.21	0.00
Overall^a	n=400	n=150	n=400	n=150	n=400	n=150	n=400	n=150
1%	1.80	22.15	90.95	44.30	0.27	0.00	0.00	0.00
5%	0.00	0.05	100.00	99.59	99.06	13.22	0.00	0.00
10%	0.00	0.00	100.00	100.00	100.00	89.40	4.36	0.00
15%	0.00	0.03	100.00	100.00	100.00	99.86	91.06	0.00
25%	0.00	0.00	100.00	100.00	100.00	100.00	100.00	0.85

^a Sample sizes in the table based on the proposed cohort sizes and study design. For example, Cohort 1 will include approximately 150 participants, with 2:1 randomization, there will be 100 participants in the VR arm and 50 participants in the Truvada arm.

An alternative way of describing the statistical properties of the study design is in terms of the 95% confidence interval for the “true” rate based on the observed data. The table below shows the exact 2-sided 95% confidence intervals for the probability of an event based on a particular observed rate. For example, if none of the 400 participants receiving the VR regimen experience a safety event, the 95% exact 2-sided upper confidence bound for the true rate of such events in a particular arm of the study is 0.92%.

Table 2. Confidence intervals for endpoint rate (proportion of participants with endpoint) given number of endpoints (rows) in with number of participants (columns)

Number of events	Number of participants ^a				
	n=50	n=100	n=150	n=200	n=400
0	0.00, 7.11	0.00, 3.62	0.00, 2.43	0.00, 1.83	0.00, 0.92
1	0.05, 10.65	0.03, 5.45	0.00, 3.66	0.01, 2.75	0.00, 1.38
2	0.49, 13.71	0.24, 7.04	0.16, 4.73	0.12, 3.57	0.06, 1.79
3	1.25, 16.55	0.62, 8.52	0.41, 5.73	0.31, 4.32	0.15, 2.18
4	2.22, 19.23	1.10, 9.93	0.73, 6.69	0.55, 5.04	0.27, 2.54
5	3.33, 21.81	1.64, 11.28	1.09, 7.61	0.82, 5.74	0.41, 2.89

Number of events	Number of participants ^a				
	n=50	n=100	n=150	n=200	n=400
6	4.53, 24.31	2.23, 12.60	1.48, 8.50	1.11, 6.42	0.55, 3.24
8	7.17, 29.11	3.52, 15.16	2.33, 10.24	1.74, 7.73	0.87, 3.90
10	10.03, 33.72	4.90, 17.62	3.24, 11.92	2.42, 9.00	1.21, 4.55
12	13.06, 38.17	6.36, 20.02	4.20, 13.56	3.14, 10.25	1.56, 5.18
15	17.86, 44.61	8.65, 23.53	5.71, 15.96	4.26, 12.07	2.11, 6.11
20	26.41, 54.82	12.67, 29.18	8.34, 19.84	6.22, 15.02	3.08, 7.62
30	45.18, 73.59	21.24, 39.98	13.92, 27.30	10.35, 20.72	5.12, 10.53

^aSample sizes in the table based on the proposed cohort size and study design.

Based on pregnancy outcome data from previous studies, we expect certain pregnancy outcomes such as premature live birth and pregnancy loss \geq 20 weeks to occur at a low frequency (5% and 2-3%, respectively). Among all women who became pregnant in MTN-003 (VOICE) and MTN-020 (ASPIRE), pregnancy loss $<$ 20 weeks was between 19-22%. Given the enrollment criteria for this study, it is expected that the frequency of pregnancy loss $<$ 20 weeks will be lower in enrolled MTN-042 participants. As such, the probability and confidence interval estimates presented in Table 1 and Table 2 also apply to estimates of the frequency of pregnancy outcomes. For example, if there was one stillbirth among the 100 participants in Cohort 1 receiving the VR regimen, the stillbirth frequency would be 1.00% and the 95% exact 2-sided confidence interval would be (0.03, 5.45).

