2.1 General Design Considerations

The following is a summary of Protocol Version 2.0

Short Title:	DELIVER: A Phase 3b Safety Study of the Dapivirine Ring and PrEP in Pregnant Women
IND Sponsor:	DAIDS
Funders:	Division of AIDS, NIAID, NIMH, NICHD, US NIH
Protocol Chair:	[name], MPH [name], MMed
Protocol Co-Chair:	[name], FCPaeds
Sample Size:	Approximately 550 women and their infants
Study Population:	Healthy, HIV-uninfected pregnant females, 18-40 (inclusive) years old, with an uncomplicated singleton pregnancy who are willing to be randomized to study product, and their infants
Study Sites:	MTN-042 site(s) selected by the MTN Executive Committee
Study Hypotheses:	
 • Daily use of Truvada oral tablet and dapivirine (DPV) vaginal matrix ring (25 mg) inserted once every 4 weeks will both be generally safe and well-tolerated by the participants and their fetuses/infants. • Participants who use Truvada oral tablet daily and insert the DPV vaginal matrix ring (25 mg) once every 4 weeks will experience similar distributions of pregnancy outcomes to the general population.
Study Design:	Phase 3b, two-arm, open label, multi-site, randomized (2:1) trial (DPV vaginal ring [VR], Truvada oral tablet), with onset of dosing period to occur within the following gestational age (GA) ranges: 
Cohort 1: 36 0/7 weeks – 37 6/7 weeks 150 women Cohort 2: 30 0/7 weeks – 35 6/7 weeks 150 women Cohort 3: 12 0/7 weeks – 29 6/7 weeks 150 women

Study Duration:	The total duration of study participation for each participant will vary depending on gestational age at time of enrollment and length of pregnancy prior to pregnancy outcome, and will range from approximately 12 weeks or less for Cohort 1 to approximately 36 weeks or less for Cohort 3. Participants who

become infected with HIV will continue in study follow-up with a modified study visit/procedure schedule for a minimum of twelve months. Also, infants born to MTN-042 participants will be followed for approximately 52 weeks (i.e., one year)

Study Products:

- Silicone elastomer matrix VR containing 25 mg of DPV
- Oral tablets (Truvada) containing 200 mg emtricitabine/300 mg tenofovir disoproxil fumarate (FTC/TDF)

Study Regimen:

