Within Cohorts 1 and 2, participants will be randomized to the above study products in a 2:1 ratio (VR:tablet). Cohort 3 participants will be randomized to the above study products in a 4:1 ratio (200 VR:50 tablet). Participants randomized to the DPV VR will use one VR continuously for approximately one month, replacing the VR each month. Participants using Truvada tablet will take one tablet orally per day. Participants will use their assigned study product until their pregnancy outcome but no later than 41 6/7 weeks of gestation.

Figure 1: Study Visit Schedule – Cohort 2

Cohort 2	Screening
Enrollment Window	Enrollment
30 0/7 weeks of gestation – 35 6/7 weeks of gestation	1-week (phone, home or clinic as needed per local standard of care)
	2-week
	3-week (phone, home or clinic as needed per local standard of care)
	4-week
	Every odd-numbered week after 36th week of gestation (e.g., follow-up weeks 5, 7, 9) until pregnancy outcome (phone, home or clinic as needed per local standard of care)
	Every even-numbered week including and after 36th week of gestation (e.g., follow-up weeks 6, 8, 10) until pregnancy outcome
Infants enroll →	Post-pregnancy outcome visit (delivery hospital/facility or clinic)
	1-week post-pregnancy outcome (phone, home or clinic as needed per local standard of care)
Mothers exit →	Approximately 6 weeks post-pregnancy outcome
	Approximately 6 months post-delivery
	Approximately 12 months post-delivery

The primary objective of the IRP is to monitor the safety of the products being evaluated and make recommendations about the continuation, modification, or termination of either or both arms of the study in the next gestational age cohort.

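### Table 1 misstates the trial's detection probabilities: the Overall P(≥1) column holds P(≥2), the ≥10 and ≥50 columns behave as >10 and >50, and the Section 2.1 Study Design row conflicts with the rest of the SAP on Cohort 3

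*SAP*

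**What the plan says.** Section 2.6 plans no formal test between arms for the primary analyses and describes the design through two tables. Table 1 "presents the probability of observing zero, at least one, ten or more, and fifty or more safety endpoints in each group", by cohort size and overall, "for various “true” event rates, ranging from low to high" (1, 5, 10, 15 and 25%).

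The arm sizes are stated as follows:
- **Cohorts 1 and 2:** the Table 1 footnote says, for Cohort 1, that "there will be 100 participants in the VR arm and 50 participants in the Truvada arm".
- **Cohort 3:** the regimen text in Section 2.1 says "Cohort 3 participants will be randomized to the above study products in a 4:1 ratio (200 VR:50 tablet").
- **Overall:** the Table 1 header gives 400 and 150, and the text before Table 2 agrees ("if none of the 400 participants receiving the VR regimen experience a safety event").

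The Overall row at 1% begins "1.80 22.15 90.95 44.30 0.27 0.00": P(0) for n=400 and n=150, then P(≥1) for each, then P(≥10) for each. The Cohorts 1-2 row at 10% includes "100.00 99.48 41.68 0.94", whose last two figures are P(≥10) for n=100 and n=50.

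The Study Design row of Section 2.1 describes the whole trial as randomized 2:1 and lists Cohort 3 as "12 0/7 weeks – 29 6/7 weeks 150 women". The same section gives a total of about 550 women. Section 2.3 gives 4:1 for Cohort 3.

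**The concern.** P(0) and P(≥1) must sum to 100%. They do in the two cohort blocks but not in the Overall block, where the 1% row gives 92.75 and 66.45. That alone shows an error without any recomputation, and it makes the tail columns worth checking.

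Table 1 is where the SAP states the probability of seeing events at given true rates. Section 2.6 also applies it to pregnancy outcomes, with expected frequencies of 5% for premature live birth and 2-3% for loss at 20 weeks or later. The affected 1% and 5% rows are therefore the relevant ones. As printed, the pooled Truvada arm looks more likely than not to miss a 1% event. In fact the chance of seeing at least one is about 78%.

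The Section 2.1 conflict is a separate matter. A reader who relies on the Study Design row gets a different Cohort 3 size and allocation from the one on which Table 1 is built.

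**Working it through.** **Inputs.** Arm sizes n = 50, 100, 150, 200 and 400, and event rates p = 1, 5, 10, 15 and 25%, all from Section 2.6. Events are binomial(n, p).

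**Formulas.** P(0) = (1−p)^n. P(X≥k) = 1 − BinomCDF(k−1; n, p). Using BinomCDF(k; n, p) instead gives P(X>k) = P(X≥k+1).

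**Step 1: the parts that reproduce.** In the cohort blocks P(0) and P(≥1) are right. For example, at n=100, 1%, 0.99^100 = 36.60% and the complement is 63.40%, as printed.

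**Step 2: the Overall P(≥1) column (%).** P(≥2) = 100 − P(0) − P(1), with P(1) = n·p·(1−p)^(n−1).

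| n, p | P(0) | P(1) | P(≥1) correct | P(≥2) | Printed as P(≥1) |
|---|---|---|---|---|---|
| 400, 1% | 1.80 | 7.25 | 98.20 | 90.95 | 90.95 |
| 150, 1% | 22.15 | 33.55 | 77.85 | 44.30 | 44.30 |
| 150, 5% | 0.05 | 0.36 | 99.95 | 99.59 | 99.59 |

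Each printed value is P(≥2). The other Overall cells in this column are 100.00 under either definition.

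**Step 3: the ≥10 and ≥50 columns (%).** Cells with the clearest differences:

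| Column | n, p | Correct for the label | Strict inequality | Printed |
|---|---|---|---|---|
| ≥10 | 100, 5% | 2.82 | 1.15 | 1.15 |
| ≥10 | 100, 10% | 54.87 | 41.68 | 41.68 |
| ≥10 | 100, 15% | 94.49 | 90.06 | 90.06 |
| ≥10 | 50, 15% | 20.89 | 11.99 | 11.99 |
| ≥10 | 50, 25% | 83.63 | 73.78 | 73.78 |
| ≥10 | 200, 5% | 54.53 | 41.69 | 41.69 |
| ≥10 | 150, 5% | 21.91 | 13.22 | 13.22 |
| ≥10 | 150, 10% | 94.00 | 89.40 | 89.40 |
| ≥50 | 200, 25% | 52.71 | 46.21 | 46.21 |
| ≥50 | 400, 10% | 6.01 | 4.36 | 4.36 |
| ≥50 | 400, 15% | 93.21 | 91.06 | 91.06 |
| ≥50 | 150, 25% | 1.36 | 0.85 | 0.85 |

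There are 25 distinct (n, p) pairs. In the ≥10 columns, 15 pairs distinguish the two definitions at two decimals, and all 15 fit >10. In the ≥50 columns, 5 pairs distinguish them, and all 5 fit >50. Of the remaining pairs, all but one agree with both definitions; the exception is the first cell in Step 4. Seven ≥10 pairs and two ≥50 pairs are off by more than 2 points. The largest gap is 54.87 − 41.68 = 13.19 points.

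**Step 4: two isolated cells.**
- ≥50 at n=100, 25% is printed 0.07. P(≥50) and P(≥51) are both below 0.00001%, so the entry fits neither definition and should be 0.00.
- Overall P(0) at n=150, 15% is printed 0.03. 0.85^150 is 0.00% to two decimals, whereas 0.85^50 = 0.03%, the n=50 value. The same row prints P(≥1) as 100.00.

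**Step 5: cohort sizes.** The Study Design row gives 150 + 150 + 150 = 450, not 550. The 200:50 regimen text gives 150 + 150 + 250 = 550, with ring 100 + 100 + 200 = 400 and tablet 50 + 50 + 50 = 150. These match the Table 1 headers.

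**The case against.** The strongest reply is that little depends on the table. The analyses are descriptive, no rule or analysis in Sections 8 to 10 uses a Table 1 value, and the observed data will get exact binomial intervals whatever the table says. Table 2 separately describes precision, for example upper limits of 0.92% (n=400) and 2.43% (n=150) with no events. The slips from ≥ to > all understate the chance of seeing events, so they do not flatter the design. The correct P(≥1) can be read off the printed P(0). The large Overall discrepancies are two cells, and the operative Cohort 3 design is clear from three other places. All of this stands. It limits the severity but does not make the printed figures right.

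Three stronger readings are tempting and are not supported:
- **That every tail cell is a strict-inequality value.** The 0.07 cell fits neither definition, and many cells are 0 or 100 under both, so they cannot show which was used.
- **That Table 1 is the SAP's only description of what the design can show.** Table 2 is offered as an alternative description.
- **That Section 2.1 is wrong throughout on Cohort 3.** Its regimen text and total agree with the other sections; only the Study Design row conflicts.

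A labelling convention does not explain the pattern either. The P(≥1) label is used correctly in the cohort blocks, and the text spells out ten or more and fifty or more.

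**Conclusion.** The point holds as a correction that should be made, not as a critical flaw. Table 1 states probabilities that the design does not have. The largest error is P(≥1) at 1% in the pooled Truvada arm: 44.30 printed against 77.85, or 33.55 points too low. The pooled ring arm is 98.20 − 90.95 = 7.25 points too low. Tail-column errors reach 13.2 points. Apart from the 0.07 cell, the tail errors understate detection, so the sample size is not put in doubt and no planned analysis changes. The Study Design row of Section 2.1 is an internal inconsistency of 100 women and of the allocation ratio in Cohort 3.

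This rests on the binomial model, which reproduces the correct cells of the table, and on the arm sizes in the Table 1 headers.

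**What to change.** - Recompute the whole of Table 1, with P(0) = (1−p)^n and, in all three tail columns, P(X≥k) = 1 − BinomCDF(k−1; n, p) for k = 1, 10 and 50. This also corrects the 0.07 and 0.03 cells to 0.00. Relabelling the tail columns as strict inequalities would not be enough, because it leaves those two cells wrong and makes the Overall block report a different quantity from the cohort blocks.
- Reconcile the Study Design row of Section 2.1 with the rest of the SAP: Cohort 3 = 250 women, and 2:1 in Cohorts 1-2 with 4:1 in Cohort 3, so that 150 + 150 + 250 = 550.
- Carry the corrected table into any report that reuses it.

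The cost is one recomputed table and one edited row. Data, conduct and planned analyses are unaffected.

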3. GENERAL DATA ANALYSIS CONSIDERATIONS

3.1 Analysis Set(s)

The ITT Analysis Set will consist of all enrolled and randomized women, and all enrolled infants. Participant treatment for mothers will be determined according to their randomization arm assignment. Participant treatment for infants will be determined according to their mother's randomization arm assignment.

A secondary Product Exposure Set will be used for some analyses and will differ from the ITT Analysis Set in that participants who never received any study product (per the Pharmacy Dispensation CRF) and endpoints that occur $>$ 7 days after study product discontinuation (per the Discontinuation of Study Product CRF) will be excluded.

A secondary Infant Exposure Set will be used for some analyses and will be the same as the ITT Analysis Set except that infants whose mothers never received study product will be excluded. If all enrolled and randomized mothers in a cohort received study product then the Infant Exposure Set and Infant ITT Analysis Set will be identical, and analyses using the Infant Exposure Set will not be performed.

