2.2 Study Objectives and Endpoints

Primary Objectives:

Maternal and Infant Safety: To describe the maternal and infant safety profile associated with

study product exposure during pregnancy

Pregnancy Outcomes: To describe the pregnancy outcomes associated with study product exposure during pregnancy

Primary Endpoints:

-

Maternal Safety (composite)

- All serious adverse events, including maternal deaths
- All Grade 3 or higher adverse events (AE) as defined by the Division of AIDS (DAIDS) Table for Grading the Severity of Adult and Pediatric Adverse Events, Corrected Version 2.1, July 2017 and/or Addendum 1 (Female Genital Grading Table for Use in Microbicide Studies [Dated November 2007])

Infant Safety (composite)

- All serious adverse events, including infant deaths and congenital anomalies
- All Grade 3 or higher AEs as defined by the Division of AIDS (DAIDS) Table for Grading the Severity of Adult and Pediatric Adverse Events, Corrected Version 2.1, July 2017

Pregnancy Outcomes

- Frequency of the following pregnancy outcomes:
 - Full term live birth (≥ 37 0/7 weeks)
 - Premature live birth (< 37 0/7 weeks)
 - Pregnancy loss (≥ 20 0/7 weeks)
 - Pregnancy loss (< 20 0/7 weeks)

Secondary Objectives:

Pregnancy Complications: To describe pregnancy complications associated with study product exposure during pregnancy

Infant Drug Levels: To describe infant levels of study drugs associated with study product exposure during pregnancy

Adherence: To characterize adherence to open label use of the DPV VR (25 mg) and oral Truvada in pregnant women

Acceptability: To characterize acceptability of open label use of the DPV VR (25 mg) and oral Truvada in pregnant women

Secondary Endpoints:

Pregnancy Complications

- Frequency of the following pregnancy complications:
 - Hypertensive disorders of pregnancy
 - Chorioamnionitis
 - Puerperal sepsis and endometritis
 - Antepartum, intrapartum and postpartum hemorrhage
 - Preterm premature rupture of membranes (PROM)
 - Fever of unclear etiology

Infant Drug Levels

- Infant blood tenofovir diphosphate (TFV-DP) and emtricitabine triphosphate (FTCTP) concentrations
- Infant plasma DPV concentrations

Adherence

- Maternal blood TFV-DP and FTC-TP concentrations
- Maternal plasma DPV concentrations
- Participant report of frequency of study product use (e.g., missed doses for oral Truvada and VR removal/expulsions [voluntary and involuntary] and duration without VR in vagina)

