6. TRIAL PARTICIPANT DISPOSITION

6.1 Disposition of Participants

The number of pregnant women screened, screened out (with reasons for not enrolling), randomized to each study arm (with reasons for not receiving assigned intervention), with obtainable pregnancy outcomes (with reasons outcome was not obtainable), completing study follow-up (with reasons study follow-up was not completed), the number of infants enrolled (with reasons not enrolled), and number of infants completing study follow-up (with reasons infant follow-up was not completed) will be presented in a CONSORT flow diagram. Separate diagrams will be used for each cohort.

Figure 1. Mock CONSORT Diagram

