8.2 Primary Infant Safety

The primary infant safety endpoint is all infant adverse events that were either SAEs or were Grade 3 or higher. These are referred to in this document as “composite AEs”.

The number and percentage of infants experiencing at least one composite AE and the exact binomial confidence intervals for those proportions will be summarized by study arm and overall for each of the three cohorts (including an exploratory analysis that splits Cohort 3 based on gestational age as described in Section 5), and by study arm and overall for the three cohorts combined. This analysis will include all infants in the ITT Analysis Set (as appropriate given the cohort/study arm being summarized).

Secondary analyses will be conducted to further explore infant safety. These analyses include:

1. The analyses in the preceding paragraph will be repeated using the Infant Exposure Analysis Set.
2. Summaries of the total number of primary infant safety endpoints reported per infant, by study arm and overall for each of the three cohorts (including a summary of the two Cohort 3 subgroups defined in Section 5), and by study arm and overall for the three cohorts combined. This will use the ITT Analysis Set.
3. A Poisson regression model will be fitted comparing the number of primary infant safety endpoints per participant by arm, adjusted for site, with an offset of the number of days from birth to study termination (see “infant study duration” definition in Section 6.2). This model will be fitted for all cohorts combined only, and will use the ITT Analysis Set.

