Visit 103 - 6-Week PPO Visit/SEV	42 days after PO	13 days prior to target	13 days after target

*The 1-Week PPO Phone Contact may be skipped if the PPO Visit occurs within the visit window for this phone contact

Table 11: Visit Timing Requirements for Infants

Visit	Target Day	Window Opens	Window Closes
V201 - PPO Visit	as soon after the PO as possible	Pregnancy Outcome	14 days after target
V202 - 1-Week PPO Phone Contact	7 days after PO	6 days prior to target	7 days after target
V203 - 6-Week PPO Visit	42 days after PO	13 days prior to target	13 days after target
V204 - 6-Month PPO Visit	183 days after PO	28 days prior to target	28 days after target
V205 - 12-Month PPO Visit	365 days after PO	28 days prior to target	28 days after target

*The 1-Week PPO Phone Contact may be skipped if the PPO Visit occurs within the visit window for this phone contact

14. APPENDIX III Residual Drug Levels Calculation

The DPV release rate per 28 days of use is calculated as:

$$rate = \frac{(conc_m - conc_r)}{days} \times 28$$

With $conc_m$ being the amount of residual drug in the manufacturer lot, $conc_r$ being the amount of residual drug in the returned ring, and $days$ being the number of days the participant should have been using the ring.

An individual ring is identified in the lab residual DPV data using the `guspec` identifier, with each individual ring having its own unique identifier. Some rings were tested multiple times and will have multiple observations with the same `guspec` value. Observations with censor values of "(A)X", "(A) X", "(B)X", "(B) X", "(B)Z", "(B) Z", or "Z" should not be analyzed. The amount of residual dapivirine in the ring ($conc_r$ above) is indicated by the value of `conc`.

Rings from the lab residual DPV data are linked to the clinical data through the Ring Insertion and Removal CRF, using the participant ID (`ptid`) and specimen collection date (`spcdt`) from the lab data and participant ID and the “Date ring returned” from the CRF data. For participants with multiple rings collected on the same date (i.e., two observations with same `ptid` and `spcdt` and different `guspec`), one ring needs to be assigned to correspond to “ring #1” in the Ring Return section of the CRF, and one to “ring #2”. In this case, the lab observation with the smaller value of `recnum` will be linked to the earlier ring return date on the CRF, and the larger value of `recnum` will be linked to the later ring return date.

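### The primary infant safety set holds only enrolled infants, so a live-born infant who dies before the enrolment visit can be missing from an endpoint that includes death

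*SAP*

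**What the plan says.** - **Analysis set.** SAP section 3.1: "The ITT Analysis Set will consist of all enrolled and randomized women, and all enrolled infants". Women enter by randomization; infants enter by a later step, their own enrolment.
- **Endpoint.** Section 2.2 lists among the components of the infant composite: "All serious adverse events, including infant deaths and congenital anomalies".
- **Where the endpoint is computed.** Section 8.2: "This analysis will include all infants in the ITT Analysis Set (as appropriate given the cohort/study arm being summarized".
- **When infants enrol.** In the Cohort 2 schedule in section 2.1, the label "Infants enroll" stands against the row "Post-pregnancy outcome visit (delivery hospital/facility or clinic". Appendix II, Table 11, which covers all infants, gives the window: "V201 - PPO Visit as soon after the PO as possible Pregnancy Outcome 14 days after target".
- **Infants who do not enrol.** Section 6.1 foresees them. The CONSORT diagram is to show "the number of infants enrolled (with reasons not enrolled", by cohort. No other rule applies to them.
- **Other infant set.** The Infant Exposure Set in section 3.1 is the enrolled set minus infants of mothers who never received product, so it cannot bring unenrolled infants back.
- **Live births.** Section 8.3 counts every obtainable pregnancy outcome and has no category for neonatal death.
- **Time origin.** Infant study duration (section 6.2) and the infant Poisson offset (section 8.2) both start at birth.

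**The concern.** The infant set carries the ITT label, but membership depends on something that happens after birth. Follow-up time starts at birth, while entry to the set requires enrolment, which may come days later. If an infant dies in between and is not enrolled, two primary endpoints treat that infant differently: section 8.3 records a full-term or premature live birth, and section 8.2 records nothing, in numerator or denominator.

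The main output of this descriptive safety study is a proportion with an exact interval for each arm. Dropping a known death changes that output directly. It can turn a rate with a lower limit above zero into one that reads as no deaths observed. The loss could also differ between cohorts or arms if early deaths do.

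**Working it through.** **The plan's own figure.** The exact (Clopper-Pearson) upper 95% limit for 0 events in n is 1 − 0.025^(1/n). For n = 400 this is 0.92%, as section 2.6 states. For n = 150 it is 2.43%, as in Table 2.

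**Inputs.** Arm totals of 400 (ring) and 150 (Truvada) come from section 2.6. Three things are assumptions, because the SAP gives no figures for them: one live birth per woman, the number k of live-born infants who die before enrolment and are not enrolled, and the number of composite events among enrolled infants.

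**Formulas.** For x events in n, the lower limit is the 2.5% quantile of Beta(x, n − x + 1) and the upper limit is the 97.5% quantile of Beta(x + 1, n − x). The SAP set uses n − k infants and omits the k deaths. The live-birth set uses n infants and counts them.

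**Death component, with no deaths after enrolment:**

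| Arm | k | SAP set: upper limit | Live-birth set |
|---|---|---|---|
| Ring, 400 | 0 | 0/400: 0.92% | identical |
| Ring, 400 | 2 | 0/398: 0.92% | 0.50% (0.06 to 1.79) |
| Ring, 400 | 4 | 0/396: 0.93% | 1.00% (0.27 to 2.54) |
| Ring, 400 | 8 | 0/392: 0.94% | 2.00% (0.87 to 3.90) |
| Truvada, 150 | 2 | 0/148: 2.46% | 1.33% (0.16 to 4.73) |
| Truvada, 150 | 4 | 0/146: 2.49% | 2.67% (0.73 to 6.69) |
| Truvada, 150 | 8 | 0/142: 2.56% | 5.33% (2.33 to 10.24) |

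The live-birth intervals for k of 2 or more can be read from SAP Table 2.

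**Whole composite, ring arm, 20 events assumed among enrolled infants:**

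| k | SAP set | Live-birth set |
|---|---|---|
| 2 | 20/398 = 5.03% (3.10 to 7.65) | 22/400 = 5.50% (3.48 to 8.21) |
| 4 | 20/396 = 5.05% (3.11 to 7.69) | 24/400 = 6.00% (3.88 to 8.80) |
| 8 | 20/392 = 5.10% (3.14 to 7.77) | 28/400 = 7.00% (4.70 to 9.96) |

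**Infants lost before enrolment with unknown status, ring arm, same 20 events, m lost:**

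| m | SAP set | Best case (none had an event) | Worst case (all had an event) |
|---|---|---|---|
| 4 | 20/396 = 5.05% | 20/400 = 5.00% | 24/400 = 6.00% |
| 8 | 20/392 = 5.10% | 20/400 = 5.00% | 28/400 = 7.00% |
| 20 | 20/380 = 5.26% | 20/400 = 5.00% | 40/400 = 10.00% |

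The SAP rate always lies between the bounds. It is too low if the lost infants had a higher event rate than the enrolled ones, and too high if they had a lower one.

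**The case against.** The strongest reply is that the SAP never says an infant who has died cannot be enrolled. Infant consent and enrolment rules normally sit in the protocol, and the SAP's use of birth as the start of infant study time hints that infants may count as on study from then. If the protocol does enrol infants who die before the visit, the death part of this point falls away. That stands as a condition. The SAP would still do well to state the rule, because it defines a primary denominator.

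Other points that stand:

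- The enrolment label appears in the Cohort 2 schedule only.
- Fourteen days is the outer limit. The target is "as soon after the PO as possible", and the visit may take place at the delivery facility, so few infants, or none, may be affected.
- A death before enrolment would probably surface as a reason in the CONSORT diagram. It would be missing from the rate, not necessarily from the report.
- The primary analyses are descriptive, with no test between arms, and the composite intervals above overlap heavily.

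A reader might infer more than the SAP supports, in three ways:

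- *That the primary infant rate as a whole is biased low.* This follows for known deaths that are left out. For infants lost with unknown status the direction is open.
- *That the Poisson offset should start at enrolment to remove time in which enrolled infants could not have died.* At most this concerns 14 of 366 days (3.8%) for an infant followed to day 365. Moving the start would remove the person-time that belongs to non-fatal events and anomalies in the first days of life.
- *That anomalies in unenrolled infants can be taken from the Pregnancy Outcome CRF.* The items that section 9.1 lists from that form include no named anomaly item.

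**Conclusion.** The point holds in a conditional form. Unless the protocol enrols infants who die before the post-pregnancy-outcome visit, sections 3.1 and 8.2 leave a known early death out of a primary endpoint that names death, while section 8.3 counts the same infant as a live birth. No other set, rule or sensitivity analysis in the SAP restores it.

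The size cannot be stated from the SAP. With 2 to 8 assumed early deaths in the ring arm, the death proportion would be 0.50% to 2.00% instead of 0%. With 20 assumed events among enrolled infants, the composite would be 5.50% to 7.00% instead of 5.03% to 5.10%. With no such deaths and no losses before enrolment, nothing changes.

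This should be fixed, because the change is cheap and concerns a primary denominator. It does not by itself cast doubt on the trial's results.

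**What to change.** 1. In sections 3.1 and 8.2, define the primary infant set as all live-born infants of randomized women, analysed by the mother's arm.
2. Count any known death from birth as a composite event, and likewise any congenital anomaly already recorded in trial data.
3. List live-born, unenrolled infants by arm and cohort, with vital status and reason for not enrolling.
4. For those with unknown status, give best-case and worst-case bounds. A live-birth denominator alone would silently score them as event-free.
5. Keep the enrolled-infant analysis as a supporting table under a name other than ITT.
6. Leave the Poisson offset starting at birth. For an added infant with a known death, state that time ends at the date of death, since section 6.2 relies on a study exit or visit record that may not exist.
7. If the protocol already enrols infants who die before the visit, say so in section 3.1.

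The cost is SAP wording and one further table, provided vital status is held for unenrolled infants. The small downside is that non-fatal events in infants who never enrolled remain unknown; the bounds and a footnote should show this.
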